5.3 Per-Protocol (PP) Population

The PP (or protocol-adherent) population is a subset of the m-ITT population, *i.e.* all trial participants who are confirmed as HIV-1 negative at the enrollment visit, with no major protocol deviations, as defined in Section 7.2.

6 GENERAL STATISTICAL CONSIDERATIONS

6.1 Analysis Software

Statistical analyses will be conducted by an external statistical service provider (Clindata Research Innovation) and reviewed by the International Partnership for Microbicides (IPM). The analyses will be performed using SAS® for Windows (version 9.3 or higher, SAS Institute Inc., Cary, North Carolina, USA).

6.2 Methods for Handling Missing Data

While every effort will be made to minimise the amount of missing data, some degree of missing data, primarily associated with missed visits, is expected. The amount of missing data will be explored and incorporated into the analyses, where appropriate. For the analysis of adherence to monthly ring use, patterns of missing data may be informative. Depending on the proportion of participants who discontinue early, an analysis of time to discontinuation may be conducted. Such an analysis would allow investigation of the covariates associated with early discontinuation. Patterns of missing data may also provide further insight into participants' preference for monthly or 3-monthly follow-up visits to research centres.

6.3 Multiple Comparisons and Multiplicity

The primary safety analysis is a descriptive analysis of the proportion of participants experiencing AEs. The primary adherence analysis is also descriptive in nature. As a result, no adjustments are required for multiplicity.

6.4 Multicentre Trials

Differences in participant safety and adherence to the dapivirine vaginal ring across research centres will be explored graphically and descriptively. The safety and adherence analyses will be summarised overall and for each research centre separately.

6.5 Planned Subgroups, Interactions, and Covariates

The analysis of the HIV-1 seroconversion rate will be based on the m-ITT population, and the primary virology analysis of drug resistance will be based on the virology population. It is expected that women with pre-existing conditions (e.g. women with STIs at Screening) will be treated and evaluated before or at enrolment into the trial, therefore no baseline adjustments are planned prospectively; however, all data will be reviewed to assess any potentially relevant baseline imbalances between research centres.

Unless specified otherwise, statistical models will include research centre as main effect. Kaplan-Meier survival curves will be produced overall and by research centre, if possible.

The following subgroup analysis will be performed for the primary safety endpoint (AEs related to Investigational Product (IP), Grade 3 and 4 AEs and SAEs):

1. Participants in the age group < 25 years, and \geq 25 years

The following subgroup analysis will be performed for the primary adherence endpoint (residual amounts of dapivirine in returned rings):

1. Participant age at baseline (< 25 *versus* ≥ 25 years)
2. Marital status at baseline (married *versus* not married)
3. Has a main sex partner at baseline (yes *versus* no)
4. Presence of genital symptoms/Sexually Transmitted Infections (STIs) at baseline (yes *versus* no)

6.6 Data Presentations

Descriptive statistics will be presented overall and by research centre.

For continuous variables, the descriptive statistics will include, but not be limited to, mean and standard deviation (SD) (when appropriate), quartiles, range, and number of observations. For categorical variables, descriptive statistics may include frequencies, relative frequencies, and the number of observations.

Derived data where it is known in advance the result will be an integer (e.g. study day) will be presented with no decimal places. Means, medians and quartiles will be displayed to one more decimal place than the source data, dispersion statistics (e.g. standard deviation) will have two more decimal places, and the minimum and maximum will be displayed to the same number of decimal places as reported in the raw data. Percentages will be presented to one decimal place (excluding 0 and 100%). When appropriate, 95% confidence intervals will be presented.

The subsequent sections discuss the planned analyses beyond the listings and simple descriptive analyses.

Baseline is defined as the last available measurement before the first insertion of the IP. All visit dates will be calculated from the enrollment visit as baseline date.

Missing or partial dates will be imputed for AEs or concomitant medication dates. No other date imputations will be performed. For AEs or concomitant medication start dates, the following conventions will be applied:

2. If only the month and year are known, then the 15th of the month will be used (*i.e.* “15” will be imputed as the day of the month) unless the month and the year equal the month and the year of the first insertion of the ring. In such cases, the same day as the day of first ring insertion will be used (to ensure that the AE or concomitant medication is considered as treatment-emergent)
3. If only the year is known, then the first day of January will be used (*i.e.* “01JAN” will be imputed as the day and month) unless the year equals the year of first ring insertion, in which case the date will be imputed with the date of first ring insertion.

For concomitant medication end dates, the following conventions will be applied:

4. If only the month and the year are known, then the last day of the month will be used
5. If only the year is known, then the last day of December (i.e. "31DEC") or the date of trial completion/discontinuation will be used (whichever comes first).

In instances where the date of IP initiation, *i.e.* the start date of ring use, is missing or unknown, the missing date will be imputed with the date of the enrollment visit.

In accordance with the protocol, each scheduled visit has a window period of \pm 7 days. If the participant does not return to the research centre for a scheduled visit prior to the start of the trial window of the next visit, the visit will be considered missed. If a participant presents for a visit outside the window for a scheduled trial visit, but prior to the start of the window for the next visit, it will be treated as a late visit. Missed visits and late visits will be documented as protocol deviations (refer to Section 7.2). Data recorded at late visits will be analysed as pertaining to the scheduled visit. Unscheduled visits may be performed at any time during the trial. If an unscheduled visit takes place within any given window period and any repeat observations are made within the given window period, the repeat values will be captured as pertaining to the unscheduled visit. Data from scheduled and unscheduled visits will be shown in the participant listings, and listings will be appropriately labelled when data arise from unscheduled visits. Data from scheduled visits will be presented in the summary tables.

Visit Schedule A will consist of participants who attend Trial Month Visits 1, 4, 7, 10, 13, and 16/Exit; Visit Schedule B will consist of participants who attend Trial Month Visits 1, 2, 5, 8, 11, 14, and 17/Exit; and Visit Schedule C will consist of participants who attend Trial Month Visits 1, 2, 3, 6, 9, 12, and 15/Exit.

Tables, figures, and listings of trial results will accompany the text of the CSR. Listings of all clinical data recorded in the CRFs will be provided, except for those CRFs which are used for administrative purposes, such as the Participant Encounter Form (PEN) and the End of Trial Inventory (ETI). Listings will be sorted by research centre and participant identification number (PID), and key variables such as visit date and/or trial visit number will be presented in each listing.

7 TRIAL PARTICIPANTS

All participants who provide informed consent for this trial will be accounted for, in accordance with ICH guideline E3 (*Structure and Content of Clinical Study Reports*)².

7.1 Disposition of Trial Participants

The number and percentage of trial participants who were screened, enrolled, received IP, permanently discontinued IP, permanently discontinued the trial, and who completed the trial will be presented, overall and by Visit Schedule (A, B or C).

For those participants who were prematurely discontinued from the trial, the time to permanent discontinuation of IP and the time to permanent discontinuation from the trial will be calculated, and presented together with Kaplan-Meier curves overall and, if appropriate, by research centre, and baseline covariates where appropriate (refer to Section 6.5; subgroups 1 to 4). Two separate probability curves will be presented;

- All reasons for premature discontinuation combined; and
- All reasons for premature discontinuation excluding seroconversion.

For participants that do not discontinue prematurely, the time to event duration will be censored as follows:

- For time to premature discontinuation of IP, the event date will be censored at the date of last known IP use
- For time to premature discontinuation from the trial, the event date will be censored at the date of last contact

For all participants the time to discontinuation from the trial (scheduled or premature) will be calculated and presented together with Kaplan-Meier curves overall and if appropriate by research centre, and baseline covariates where appropriate.

The time to an event will be calculated as follows:

- Time to event (days) = (Date of IP discontinuation/trial discontinuation/Censoring Date – Date of first ring use) + 1

A listing reflecting each participant's screening date, enrollment date, and scheduled and unscheduled visit dates, as documented in the PEN CRF, will be provided.

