Any participant who is confirmed HIV-infected while on the trial will be permanently discontinued from IP and the trial. An exit visit will be scheduled approximately 1-2 months following IP discontinuation. Initial counselling services will be provided at the research centre and women will be referred for additional counselling, support services and treatment. In addition, these women will be offered the option of enrolling for IPM's seroconverter protocol.

In an instance where a participant is determined to be HIV-seropositive (as determined by HIV rapid tests, Western Blot; and any other confirmatory tests, if applicable), but cannot be confirmed as HIV-infected (HIV RNA PCR) the participant will be discontinued from IP and the protocol-required procedures as per original trial visit schedule will be conducted at the investigator's discretion. Samples for measurement of dapivirine levels will no longer be collected. Additional testing to demonstrate HIV infection may be performed. Participants will be followed up until the exit visit according to the original enrolment date.

5.4.4. ***Exit Visit***

For participants confirmed as HIV-negative prior to the exit visit

If both HIV rapid tests (Test 1 and Test 2) are non-reactive, the participant will be considered HIV-seronegative. If both Test 1 and Test 2 are reactive, additional confirmatory testing will be performed by Western Blot and other confirmatory tests, where appropriate. Samples for possible viral genotype resistance testing and HIV-1

RNA PCR testing will be collected. Once HIV infection has been confirmed, this will be considered an HIV seroconversion after product discontinuation and may be a combination of both women infected during IP use who seroconverted after IP discontinuation, as well as women infected after IP use. Nucleic acid-amplification testing (NAAT) by a HIV-1 RNA PCR test will be performed on stored samples in reverse sequential order to estimate the time point of HIV infection.

Initial counselling services will be provided at the research centre and women will be referred for additional counselling, support services and treatment.

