5.6. Pregnancy Testing and Management

A urine pregnancy test will be performed at all scheduled trial visits, except for the Exit Visit, and can be performed additionally at unscheduled visits if any reason exists to suspect pregnancy or, in the event of a participant defaulting on her contraception, prior to recommencing contraception.

If a potential participant tests positive for pregnancy during screening, she is not eligible to enrol in the trial, but will receive referrals to prenatal clinics or other appropriate facilities.

A product hold will be implemented if a woman tests positive for pregnancy while on IP. Vaginal ring(s) will be retrieved from the participant, but the participant will not be withdrawn from the study. Protocol-specified visit schedule and procedures will continue except for IP-related procedures and other examinations if contra-indicated by pregnancy. The participant will be referred to a local prenatal clinic for medical services. The research centres will be asked to report all pregnancies to IPM within 48 hours of a positive pregnancy test or a confirmatory serum pregnancy test, if indicated. A confirmatory serum pregnancy test may be requested at the discretion of the investigator or a designated qualified member of the trial staff if reason exists to suspect a false positive urine pregnancy test. If the serum pregnancy test is negative, the investigator can consider recommencing use of the ring. If the participant indicates a change in pregnancy status or the participant's clinical history indicates a change in her pregnancy status after the product hold (birth or termination), a urine pregnancy test may be performed. A confirmatory serum pregnancy test may be requested at the discretion of the investigator or a designated qualified member of the trial staff if reason exists to suspect a false positive urine pregnancy test. If the urine pregnancy test is negative, the investigator can consider recommencing IP. The participant must have a negative urine pregnancy test prior to re-introduction of IP, and should not be breast-feeding. A pelvic examination should be performed prior to re-introduction of IP.

Women who become pregnant and HIV-positive during the trial will be referred for appropriate PMTCT services.

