14.6.3	Proportion of Participants Opting for HIV Rapid Tests at the Research Centre Between Scheduled 3-Monthly Visits
14.6.4	Social Harms
14.6.5	Participant Questionnaire – Part A (Month 1, 2, and 3)
14.6.6	Participant Questionnaire – Part B (Month 2 and 3 only)
14.6.7	Participant Questionnaire – Part C (Month 1, 2, and 3)
14.6.8	Participant Questionnaire – 3 Month Follow-Up
14.6.9	Participant Questionnaire – Last Product Use Visit
14.6.10	Participant Questionnaire - Vaginal Practices

Table 14.1.1.1
Disposition of Participants by Visit Schedule
All Participants

	Statistic	Schedule A	Schedule B	Schedule C	Unknown	All Schedules
Screened participants	N					X
Screen failures	n (%) ^a					X (X.X)
Reasons for ineligibility						
Incl /	n (%) ^b					X (X.X)
Excl /	n (%) ^b					X (X.X)
Incl and excl	n (%) ^b					X (X.X)
Participants enrolled	n (%) ^a	X (X.X)	X (X.X)	X (X.X)	X (X.X)	X (X.X)
Participants who received IP	n (%) ^c	X (X.X)	X (X.X)	X (X.X)	X (X.X)	X (X.X)
Permanently discontinued IP	n (%) ^c	X (X.X)	X (X.X)	X (X.X)	X (X.X)	X (X.X)
Permanently discontinued trial	n (%) ^c	X (X.X)	X (X.X)	X (X.X)	X (X.X)	X (X.X)
Completed trial	n (%) ^c	X (X.X)	X (X.X)	X (X.X)	X (X.X)	X (X.X)
Reason for discontinuing trial						
Non-compliance	n (%) ^d	X (X.X)	X (X.X)	X (X.X)	X (X.X)	X (X.X)
Lost to follow-up	n (%) ^d	X (X.X)	X (X.X)	X (X.X)	X (X.X)	X (X.X)
Adverse event/intercurrent illness	n (%) ^d	X (X.X)	X (X.X)	X (X.X)	X (X.X)	X (X.X)
Inappropriate enrolment	n (%) ^d	X (X.X)	X (X.X)	X (X.X)	X (X.X)	X (X.X)
HIV-1 seroconversion	n (%) ^d	X (X.X)	X (X.X)	X (X.X)	X (X.X)	X (X.X)
Pregnancy	n (%) ^d	X (X.X)	X (X.X)	X (X.X)	X (X.X)	X (X.X)
Sponsor terminated the trial	n (%) ^d	X (X.X)	X (X.X)	X (X.X)	X (X.X)	X (X.X)
Death	n (%) ^d	X (X.X)	X (X.X)	X (X.X)	X (X.X)	X (X.X)
Other	n (%) ^d	X (X.X)	X (X.X)	X (X.X)	X (X.X)	X (X.X)
Participant withdrew consent	n (%) ^d	X (X.X)	X (X.X)	X (X.X)	X (X.X)	X (X.X)
Relocation	n (%) ^e	X (X.X)	X (X.X)	X (X.X)	X (X.X)	X (X.X)
Employment/work	n (%) ^e	X (X.X)	X (X.X)	X (X.X)	X (X.X)	X (X.X)
Family/partner pressure	n (%) ^e	X (X.X)	X (X.X)	X (X.X)	X (X.X)	X (X.X)
Other	n (%) ^e	X (X.X)	X (X.X)	X (X.X)	X (X.X)	X (X.X)

Excl = Exclusion; HIV-1 = Human immunodeficiency virus type 1; Incl = Inclusion; IP = Investigational product

Percentages are calculated out of the number of participants (per visit schedule) ^a Screened ^b Screen failed ^c In the safety population ^d Non-completed ^e Withdrawn consent

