Other	X (X.X)	X (X.X)	X (X.X)	X (X.X)	X (X.X)	X (X.X)	X (X.X)	X (X.X)	X (X.X)	... X (X.X)

Programmers Note: Please repeat the table for all available Trial Months

Percentages are calculated out of the number of participants in the safety population

IPM 032

FIGURE SHELLS – VERSION 1.0, 26 MAR 2020

Number	Listing Heading
14.1	Demographics
14.1.1.1	Disposition of Participants
14.1.1.1.1	Time to Trial Discontinuation
14.1.1.1.2	Time to (Premature) Permanent Investigational Product Discontinuation
14.3	Safety Data
14.3.5.1	Adherence – Dapivirine Residual Levels in Used Rings
14.3.5.1.1	Dapivirine Ring Residual Levels (mg)
14.3.5.1.2	Dapivirine Ring Residual Levels (mg) By Trial Visit and Category of Residual Amount
14.3.5.1.3	Relating The Dapivirine Ring Residual Levels (mg) To The Time Intervals Between Consecutive Ring Replacements
14.3.5.1.4	Residual Levels of Dapivirine (mg) in The Last Three Returned Rings Prior To HIV Seroconversion VS Average Ring Residual Levels
14.3.5.1.8	Corrected Residual Levels of Dapivirine in The Last Three Returned Rings Prior To HIV Seroconversion VS Average Ring Residual Levels of HIV- Participants
14.3.7	Other Safety Data
14.3.7.7	Time to HIV-1 Seroconversion – m-ITT population
14.3.7.8	Time to HIV-1 Seroconversion – PP population
14.6	Other Data
14.6.4	Correlation Between Dapivirine Residual Amounts (mg) in Returned Used Vaginal Rings and Results From Visual Inspection of Returned Vaginal Rings

Figure 14.1.1.1.1
Kaplan-Meier Curves, Time to Trial Discontinuity
Safety Population

[figure not shown]
[figure not shown]

Figure 14.1.1.1.2
Kaplan-Meier Curves, Time to (Premature) Permanent Investigational Product Discontinuation
Safety Population

[figure not shown]
Programmers Note: Figure wil resemble F14.1.1.1 with time to permanent IP data.

Figure 14.3.5.1.1
Dapivirine Ring Residual Levels (mg)
Safety Population

[figure not shown]
Programmers Note: Please repeat for all centres.

Figure 14.3.5.1.2
 Dapivirine Ring Residual Levels (mg) By Trial Visit and Category of Residual Amount
 Safety Population

Programmers Note: Please repeat for all trial months.

Figure 14.3.5.1.3
 Relating The Dapivirine Ring Residual Levels (mg) To The Time Intervals Between Consecutive Ring Replacements
 Safety Population

Programmers Note: Please repeat for all centres.

Figure 14.3.5.1.4
Residual Levels of Dapivirine (mg) in The Last Three Returned Rings Prior To HIV Seroconversion VS Average Ring Residual Levels
Safety Population

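### SAP 7.1 ties events on the ring-discontinuation curve to leaving the trial, so read literally a woman who stops the ring for good but stays in follow-up is censored on her stop date

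*SAP*

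**What the plan says.** SAP 7.1 plans two time-to-event measures, one for IP and one for the trial. A single sentence introduces both. It begins "For those participants who were prematurely discontinued from the trial, the time to permanent discontinuation of IP", then names the matching measure for trial exit, and asks for Kaplan-Meier curves of each.

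The censoring rule follows. It opens "For participants that do not discontinue prematurely, the time to event duration will be censored as follows", and its IP bullet reads "For time to premature discontinuation of IP, the event date will be censored at the date of last known IP use". The rule does not say whether prematurely refers to the trial or to IP. A later sentence in the section extends time to trial discontinuation to all participants. No matching sentence covers IP.

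The protocol treats coming off the ring and leaving the trial as different things:

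- **Seropositive but not confirmed infected (5.4.3):** "the participant will be discontinued from IP and the protocol-required procedures as per original trial visit schedule will be conducted". The investigator has discretion over those procedures, and follow-up runs to the exit visit. The end of 5.6 confirms that such women may continue without IP.
- **Pregnancy (5.6):** "A product hold will be implemented if a woman tests positive for pregnancy while on IP". It adds "Vaginal ring(s) will be retrieved from the participant, but the participant will not be withdrawn from the study". Restart is possible later.

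The SAP also separates the two. Table 14.1.1.1 has a row "Permanently discontinued IP" apart from the row for leaving the trial. In SAP 10.1.2, Table 2 takes IP withdrawal for an adverse event from the AE form and trial withdrawal from the trial completion form.

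**The concern.** For a woman who stops the ring permanently, the date of last known IP use is her stop date. If she stays in the trial and is treated as not having discontinued prematurely, her event is replaced by a censoring on the same day. She then leaves the risk set without lowering the curve.

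The error has one direction. Dropping true events in this way can raise the persistence estimate but never lower it. It would affect both planned versions of the IP curve (all reasons, and all reasons except seroconversion). It would also affect any versions by centre or baseline covariate, where groups that differ in how often women stop but stay would be compared unfairly. SAP 6.2 names covariates of early discontinuation as a use of this kind of analysis, and Figure 14.1.1.1.2 is the only time-to-event figure for ring persistence in the list of figure shells.

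**Working it through.** The plan states no persistence or discontinuation figure, so there is nothing to reproduce. The check has three parts.

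**1. Who is off the ring but still in the trial**

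| Route | Source | Status under the literal SAP 7.1 wording |
|---|---|---|
| Seropositive, infection not confirmed | Protocol 5.4.3, 5.6 | Off IP, followed to exit: censored at the stop date |
| IP withdrawn for an AE without trial exit | SAP Table 2 (separate source forms) | Censored at the stop date |
| Pregnancy hold never lifted, no trial exit recorded | Protocol 5.6 | Censored at the date of ring retrieval |
| Pregnancy recorded as the reason for leaving the trial | Table 14.1.1.1 | Event |

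**2. Small example**

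Of 100 women, 5 leave the trial on day 100, 5 stop the ring for good on day 200 but stay in follow-up, and 90 complete day 365.

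- Literal wording: the only events are the 5 on day 100, so S(365) = 1 − 5/100 = 95%.
- Every permanent stop an event: S(365) = (1 − 5/100) × (1 − 5/95) = 90%.

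**3. Size under assumed rates**

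Neither rate is in the documents. Let p be the 12-month risk of stopping for reasons the curve captures, and h the rate per person-year of permanent stops it misses, with independent constant hazards.

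- Discontinuation shown = p
- True discontinuation = 1 − (1 − p) × exp(−h)
- Gap = (1 − p) × (1 − exp(−h))

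| p | h | Shown | True | Gap (points) |
|---|---|---|---|---|
| 8% | 0.02 | 8.0% | 9.8% | 1.8 |
| 8% | 0.06 | 8.0% | 13.4% | 5.4 |
| 12% | 0.02 | 12.0% | 13.7% | 1.7 |
| 12% | 0.06 | 12.0% | 17.1% | 5.1 |

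A second set of assumptions works from proportions. With 10% leaving the trial early by 12 months, the curve shows 90.0% persistence. If 1%, 3%, 5% or 10% stop but stay, the true figure is 0.90 × 0.99 = 89.1%, 0.90 × 0.97 = 87.3%, 0.90 × 0.95 = 85.5% or 0.90 × 0.90 = 81.0%. The overstatement is 0.9, 2.7, 4.5 or 9.0 points. Varying early trial exit from 5% to 15% gives a range of about 0.9 to 9.5 points. Simulated Kaplan-Meier curves with 1400 women and 40 replicates per setting agreed with the formula to within about 0.2 points.

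**The case against.** The strongest reply is that SAP 7.1 is loosely worded rather than wrong. The IP censoring bullet is specific to its endpoint, and the time formula lists the IP and trial discontinuation dates as alternatives. The figure shell is titled "Kaplan-Meier Curves, Time to (Premature) Permanent Investigational Product Discontinuation" and is drawn on the Safety Population. A programmer working from these could flag every permanent IP stop, whatever the trial status. This stands as a possible reading, so it cannot be said that the curve will certainly be wrong. It does not supply the missing rule: the sentence that names who has an event still refers to the trial.

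A reader might also infer that an unlifted pregnancy hold is never coded as permanent discontinuation, so that every such hold is lost. The documents give no coding rule to support that. Some wording points the other way: Protocol 5.5 tells women that pregnancy means stopping IP at once, Listing 16.2.8.9 has a response for IP stopped because of pregnancy, and pregnancy is a listed reason for leaving the trial. Whether a mandated hold should count as non-persistence is also a choice of estimand. The seropositive-but-unconfirmed woman is the cleaner example, though probably rare.

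Finally, the curve is a disposition display and not an endpoint, and Protocol 8.6 makes such an analysis optional. Covariate versions are planned only where appropriate. Table 14.1.1.1 counts permanent IP stops and Table 14.3.7.15 summarises total time on IP. This stands and limits the consequence to the IP curve and its breakdowns.

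**Conclusion.** The point holds as a defect of definition with a known direction and an unknown size. Followed literally, SAP 7.1 censors permanent ring stops that occur without trial exit on the stop date, and Figure 14.1.1.1.2 then overstates persistence. On the more lenient reading the event definition is still unstated.

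The figure of about 2 to 5 percentage points at 12 months rests on assumed rates, on independent constant hazards, and on the curve catching all other stops and none of the stop-but-stay group. It illustrates the effect and is not an estimate for this trial. The same inputs can be put as a relative understatement of discontinuation of 13% (1.7/13.7) to 40% (5.4/13.4), and a reader might take that as the size of the problem. The documents do not support it: the base is small and both rates are assumed. The matter is minor, but it should be settled in the text before the curve is programmed.

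**What to change.** In SAP 7.1, separate the two curves and define the IP curve for the whole Safety Population:

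- **Event:** permanent IP discontinuation before the scheduled last product use visit, whatever the trial status, dated at last ring removal.
- **Censoring:** women still on the ring at the scheduled last product use visit or at trial closure, at that date.
- **Lost to follow-up with unknown removal date:** state which date applies (last known IP use is one option). Without a rule these women would be given an unobserved event date.
- **Product hold with no later ring insertion:** state how it is classed for the analysis, and break events down by reason so that results with and without unresolved pregnancy holds can be seen.

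The cost is a few lines of SAP text and one reprogrammed event flag, using the ring insertion/removal log already collected. The curve may look slightly less favourable. No new data are needed.
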